#### **Study Design Rationale**

This is open label study to examine the safety, effectiveness, and tolerability of the treatment in routine clinical practice, to determine how the treatment works under ordinary and variable conditions, prescribed by clinicians with varying degrees of expertise and practicing across the spectrum of health care settings, to treat a heterogeneous group of patients.

The schedule of assessments will be as follows:

Examination	Baseline Visit 1 (Day 1)	Visit-2 (8 ± 2 weeks)	EOS Visit 3 (16 ± 2 weeks)
Informed consent	X		
Patient demographics (sex, age, etc)	X		
Relevant medical history	X		
Vitals	X	X	X
Physical examination*	X	X	X
Height** and weight	X	X	X
Inclusion/Exclusion criteria	X		
MMSE Score	X	X	X
ADCS-ADL SIV score	X		X
Concomitant medications		X	X
Treatment for AD	X	X	X
Urine examination	X	X	X
Skin irritation assessment		X	X
Patch adhesion assessment		X	X
Adverse Events (AEs)and Serious Adverse Events (SAEs) recording	X	X	X
Compliance assessment using caregiver questionnaire		X	X
EOS			X

EOS = End of Study  
X = Assessment to be recorded on CRF

\*Physical examination includes examination of general appearance, skin, neck (including thyroid), eyes (excluding fundus), ears, nose, throat, lungs, heart, abdomen, back, lymph nodes, and extremities. In addition, a neurological exam consisting of cranial nerve, motor and sensory assessments as performed in routine clinical practice. It also includes recording of pulse and blood pressure as per routine clinical care.

\*\* Height is assessed only at Visit 1

#### **7.1.2 Treatment Regimen**

The study will include the following open-label drug:

Exelon© patch: 15 cm^2 patch sizes loaded with 27 mg of rivastigmine.

	Statistical Analysis Plan Sponsor: Novartis
Study Number:	Version: Final 1.0 Date: 01 Dec 2022

## 7.2 Efficacy endpoints

Efficacy endpoints will be as follows:

### 1. Mini-Mental State Examination (MMSE):

Assessing the changes in Mini-Mental State Examination (MMSE): The MMSE is a brief, practical screening test for cognitive dysfunction (Folstein et al. 1975). The test consists of five sections (orientation, registration, attention-calculation, recall, and language & Praxis) and results in a total possible score of 30, with higher scores indicating better function. MMSE shall be recorded at the start and at each visit.

### 2. ADCS-ADL SIV SCORE:

This is a tool to assess the ability of patients with moderate to severe dementia to perform activities of daily living. ADCS-ADL SIV score is done at start and end of visit. This includes 19 questions and total score is 54. Administration instructions and Instruction card for the rater to use when administering the scale is separately provided

## 7.3 Safety Assessments

Safety endpoints will be as follows:

- Urine examination
- Skin reaction at patch
- Patch adhesion
- Adverse events.
- Compliance by Caregiver medication questionnaire

## 8 General Statistical Considerations

### 8.1 Descriptive Statistics

The following descriptive statistics will be calculated for continuous data and for ordered categorical data (ordinal data):

Summary statistics are displayed with the following digits:

Description	Characteristic	Number of decimal places
Count	n	0
Count corresponding to the number of patients for a group	N	0
Mean	Mean	As in source + 1
Standard Deviation	SD	Mean+1
Minimum	Min	As in source
Median	Median	As in source + 1
Maximum	Max	As in source
1st Quartile / 3rd Quartile	Q1/Q3	As in source + 1
Percentage relative to N #	%	1

	Statistical Analysis Plan Sponsor: Novartis
Study Number: [REDACTED]	Version: Final 1.0 Date: 01 Dec 2022

# Number of decimal places can be more than one, if necessary. All table percentages should be rounded to one decimal place if not stated otherwise.

All data will be presented in the patient data listings.

If either table or listing does not include any observation, then the following placeholder will be used: “NO DATA CONTRIBUTED TO THIS TABLE / LISTING”.

## 8.2 Analysis Population

Two population will be considered for the analysis: The intend to treat (ITT) population and safety population. Analysis for all efficacy endpoints using the ITT population will be the primary approach for analysis. For safety endpoints, safety population will be used for analysis.

Analysis Population	Definition
Screened Population	All the subjects who screened in the study will be considered
Intend to treat Population	The intend to treat (ITT) set will include all patients having signed the Informed Consent, who have at least one post baseline assessment.
Safety population	The safety set will include all patients who provide Informed Consent to collect information and who were treated with at least one patch of rivastigmine 27 mg- 15 cm  transdermal patch during this study. Of note, the statement that a patient had no AE also constitutes a safety assessment

## 8.3 Definitions

In the following table, the definitions and calculation of derived variables are summarized

Variable / Term	Definition / Way of calculation
Age	Int ((informed consent date – Birth date +1)/365.25)
Baseline	The last valid value prior to the first dose of study treatment
BMI (kg/m2)	Weight (kg) / (Height (m) x Height (m))
Duration of exposure	Treatment end date- treatment start date + 1
Treatment Start Date	Date of dose administration on Day 1 in Investigational Product Log in the CRF
Treatment End Date	The last date from the ‘Investigational Product Log’ form to be considered as treatment end date
Treatment Emergent AE (TEAE)	An AE will be considered as treatment-emergent if the time of onset is on or after the time of the first dose or any AE that exist prior to first dose and if it increased in severity during the study.

	Statistical Analysis Plan Sponsor: Novartis
Study Number: [REDACTED]	Version: Final 1.0 Date: 01 Dec 2022

## 8.4 Protocol Deviation

The relevant protocol deviations have to be defined by a systematic data review prior to database closure. For this purpose, protocol violations that occurred during the study such as violations of inclusion/exclusion criteria or forbidden concomitant medications or patient non-compliance will be assessed as ‘major’ or ‘minor’ depending on their potential to interfere with the objectives of the study. Listings will be prepared to show the eligibility of all patients. Comprehensive justification for the classification of a protocol violation/deviation as “major” will be given in the integrated clinical study report.

The protocol deviations (Major and Minor) will be summarized using frequency count and percentage and overall, using ITT Population.

The list of protocol deviations will be reviewed by the sponsor and finalized before locking the database.

## 8.5 Data Handling

### 8.5.1 Imputation of Missing data

LOCF (last observation carried forward) method will be used for missing values at week 16.

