1.1 Background

1.2 Purpose

Alzheimer's disease (AD), a progressive neurodegenerative disorder, is the most prominent cognitive disorder of the elderly. The prevalence of AD in people over the age of 65 is 5-10%, and increases up to 50% in those over the age of 85 (Small GW, 1995). The Alzheimer's Association estimates that in 2008, as many as 5.2 million Americans have AD (Alzheimer's Association, 2008).

Multiple deficits of neurotransmitters occur in the brain of AD patients. However, the most common is a decrease in levels of acetylcholine (ACh), which is due to a loss of presynaptic cholinergic nerve terminals. These cholinergic deficits are most apparent in the areas of the brain involved in memory and cognition, i.e., the frontal cortex and hippocampus (Perry et al, 1978).

Currently, there are two compounds approved in the US for the treatment of severe dementia of the Alzheimer's type, the cholinesterase inhibitor donepezil and the glutamate modifying agent memantine. Both are often used together. With only one agent in each class available to treat patients with severe dementia of the Alzheimer's type, there is significant medical need to have other approved agents available, including those that have an alternative route to oral administration.

A number of treatment strategies involving the cholinergic system have been evaluated. Cholinesterase inhibitors (ChEIs), including rivastigmine (also known as ENA713 and Exelon®), have been shown to be effective in improving cognitive and global functioning in mild to moderate AD patients (Kumar et al, 1991; Knapp et al, 1994; Rogers et al, 1998; Corey-Bloom et al, 1998; Rösler et al, 1999; Raskind et al, 2000; Tariot et al, 2000).

Memantine has established efficacy in moderate to severe dementia of the Alzheimer's type (Reisberg et al, 2003; Tariot et al, 2004; van Dyck et al, 2007) and can be used as an augmenting agent with ChEIs.

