4.6.10 Discontinuation of study treatment and premature patient withdrawal

The planned duration of the study is 16 weeks (+/- 2 weeks) and patients should be followed until the end of the study except if any of the following conditions for early termination are met:

- Voluntary discontinuation (withdrawal of consent to collect or use their data)

- Treatment discontinuation (patient no longer take the medication under observation)
- Addition of second AD treatment (patient no longer on monotherapy)

All data generated up to the time of voluntary discontinuation (withdrawal of consent) and the reason(s) for discontinuation will be recorded. Patients who choose to withdraw consent will no longer be contacted for follow up information.

Patients who discontinue treatment or patients who are no longer on monotherapy should be asked to return for an early discontinuation assessment. For patients who are lost to follow-up (i.e. those patients whose status is unclear because they fail to appear for study visits without stating an intention to withdraw), the physician should show "due diligence" by contacting the patients and asking them to return for a final assessment. Every effort should be made to obtain reason for discontinuation. The physician should document in the source documents steps taken to contact the patient, e.g. dates of telephone calls, registered letters, etc.

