#### Safety

No imputation will be done on missing safety data, unless for partially incomplete dates for remote events such as AE, concomitant medication etc.

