### 9.6.2 Secondary Analysis

- 1) To assess patient's compliance of rivastigmine 27 mg -15 cm^2 transdermal patch during 16 weeks treatment period

The Compliance by Caregiver medication questionnaire will be summarized descriptively by visit using ITT population.

- 2) To assess the skin tolerability (irritation and adhesion) during 16 weeks treatment period

Skin tolerability will be summarized by the number and percentages of patients using safety population.

- 3) To assess the proportion of patients with UTI during 16 weeks treatment period

Proportion of patients with UTI will be summarized by the number and percentages of patients using safety population.

- 4) To evaluate treatment effect by rivastigmine 27 mg -15 cm^2 transdermal patch by assessing the changes in Mini-Mental State Examination (MMSE)

The change from baseline for Week 8 and Week 16 in MMSE total score will be summarized descriptively using the ITT population and treatment for the study

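### A missing week-16 MMSE is filled with the last available score and nothing else is planned, so if leavers keep declining the week-16 decline is understated, probably slightly at the planned drop-out.

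*SAP*

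**What the plan says.** The only rule for missing efficacy data is the one line in SAP 8.5.1: "LOCF (last observation carried forward) method will be used for missing values at week 16". Protocol 8.4.3 says the same. The safety part of SAP 8.5.1 adds "No imputation will be done on missing safety data", apart from partial dates, so the LOCF rule falls on the efficacy scores. Protocol 8.4.4 states that no supportive analyses are planned, and the SAP adds none.

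The MMSE is scheduled at baseline, week 8 and week 16. SAP 9.6.2 says: "The change from baseline for Week 8 and Week 16 in MMSE total score will be summarized descriptively using the ITT population". The analysis set is defined in SAP 8.2: "The intend to treat (ITT) set will include all patients having signed the Informed Consent, who have at least one post baseline assessment". The assessment need not be an MMSE.

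Protocol 4.6.10 ends follow-up when consent is withdrawn, when the patch is stopped, or when a second AD drug is added. Patients in the last two groups are to be asked back for an early-discontinuation assessment, and patients lost to follow-up for a final one. Neither visit is in the schedule of assessments, and neither document says whether an MMSE is done there or which visit its score would count for.

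Shell Table 14.2.1 has one EOS block per MMSE section and for the total, each with a single n.

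**The concern.** Carrying a score forward fixes the later change at zero. Protocol 1.2 describes AD as "a progressive neurodegenerative disorder", so zero later change is not a neutral assumption. There is no comparator, so no between-arm contrast could offset an error: the within-group mean change is the whole MMSE result. The synopsis names MMSE change under the key secondary objective of a study that the health authority required.

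Two features make the problem hard to see. The EOS n in Table 14.2.1 would count carried scores as if they had been observed, with no line for the number imputed. Any 95% CI added under the general statement in Protocol 8 would treat those scores as real information. And because the carried value is undefined, two programmers following the SAP could produce different week-16 means.

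**Working it through.** **Inputs**
- MMSE times: baseline, week 8, week 16 (schedules in Protocol 5 and SAP 7.1.1).
- Drop-out: 10% (Protocol 8.7, SAP 8.6). The plan has no MMSE design figure. Its sample size concerns adverse-event incidence and reproduces: 1.645² × 0.746 × 0.254 / (0.10 × 0.746)² = 92.1, rounded up to 93; then 93 × 1.1 = 102.3, printed as 102. Only the 10% is used here.
- MMSE rate of decline and SD: not in the documents. Both are assumed below and shown as ranges.

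**Relative size**

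Let D be the linear decline over 16 weeks in stayers, m the share with week 8 carried forward, and r the leavers' decline rate relative to stayers.
- True mean decline = D[(1 − m) + mr]
- LOCF mean decline = D[(1 − m) + mr/2]
- Relative understatement = (mr/2) / [(1 − m) + mr]

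This is m/2 for r = 1 and m/(1 + m) for r = 2. For r = 0 it is zero; if leavers improve, the sign reverses.

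| m | r = 1 | r = 2 |
|---|---|---|
| 10% (planned drop-out) | 5.0% | 9.1% |
| 20% | 10.0% | 16.7% |
| 30% | 15.0% | 23.1% |

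The 20% and 30% rows only show how the effect grows; nothing in the documents predicts them. At the planned drop-out, m = 10% is an upper figure for the share carried from week 8, because the 10% includes leavers with no week-8 score and leavers with a later one.

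**If the carried score is not week 8**

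For a last score at week t and r = 1, the understatement is m(1 − t/16). At m = 10%:
- t = 12 (for example, an early-discontinuation score): 10% × 4/16 = 2.5%
- t = 8: 5%
- t = 0 (baseline carried): 10%

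With baseline carried and r = 2, it is 2m/(1 + m) = 0.2/1.1 = 18.2%.

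**Size in MMSE points**

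Bias = m × (annual decline) × 8/52, with an assumed decline of 2 to 6 points per year:
- m = 10%: 0.10 × 2 × 8/52 = 0.03 to 0.10 × 6 × 8/52 = 0.09
- m = 20%: 0.06 to 0.18
- m = 30%: 0.09 to 0.28
- Baseline carried, m = 10% (16/52 in place of 8/52): 0.06 to 0.18
- No change after week 8: 0. Improvement of 2 points per year, m = 10%: −0.03

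For comparison, the standard error of the mean change with an assumed SD of 2 to 4 and n = 93 is 2/√93 = 0.21 to 4/√93 = 0.41. At the planned drop-out, the bias from carrying week 8 forward is well below sampling error.

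**The case against.** The strongest reply is that this matters little. The study is single-arm with no hypothesis, its primary outcome is adverse events, and MMSE change is summarised descriptively. The Table 14.2.1 shell has no standard error, interval or test. Week-8 change is reported without imputation, and Tables 14.1.1 and 14.1.4 show part of the missingness. Most of this stands, and it limits the weight of the point. It does not supply the number of imputed MMSE scores. Nor is the bias like sampling error: no interval reflects it.

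A reader might also infer three stronger things that the documents do not support:
- *That every missing score is replaced by week 8.* The rule says last observation. Leavers are asked back, so a later and possibly poorer score may exist; those who leave before week 8 have no week-8 score.
- *That the result will look too favourable.* This requires decline after the last score. The documents give no MMSE trajectory, and Protocol 3.6 reports symptom improvement in all but one rivastigmine trial, so stability or improvement over 16 weeks is possible.
- *That missing scores concentrate in patients doing badly.* It is plausible that leaving is related to outcome, but Protocol 4.6.10 covers withdrawal of consent and stopping the patch for any reason, and poor tolerability is not cognitive decline.

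It is also fair to object that a mixed model assumes missing at random, so it does not by itself answer a worry about informative drop-out. That is right, and the fix adds a worse-decline analysis for this reason.

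**Conclusion.** The point holds in conditional form. LOCF is the sole treatment of missing week-16 MMSE scores, the carried value is not defined, and no planned output lets a reader judge the effect. If leavers continue to decline, the mean decline is understated by about 5% (equal rates) to 9% (twice the rate) with week 8 carried forward for 10% of patients. If baseline is carried for that 10%, the figures are 10% and 18%. These figures rest on linear decline and assumed relative rates. In points, carrying week 8 forward costs roughly 0.03 to 0.09 under the assumed 2 to 6 points per year.

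The effect is therefore probably small at the planned drop-out, and it leaves the primary safety result untouched. The change should be made because the data are already being collected and the cost is low. The week-16 result is not shown to be misleading.

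**What to change.** In SAP 8.5.1 and 9.6.2:
- Report the week-16 MMSE mean change with 95% CI from a mixed model for repeated measures on all observed scores, with visit as a category, baseline MMSE as covariate and unstructured covariance. State how many patients have no post-baseline MMSE, since they contribute nothing to this model.
- Show observed-case n, mean and SD beside it in Table 14.2.1.
- Keep LOCF as a labelled sensitivity analysis. Define the carried value, including whether baseline may be carried, and print the number imputed.
- Add a delta-adjusted analysis in which leavers decline faster than the model predicts, over a stated range of deltas, because the model assumes missing at random.
- State whether the early-discontinuation assessment includes an MMSE and how its score maps to visits. The scheduled windows run from weeks 6 to 10 and 14 to 18, so a score outside both needs a rule.
- Carry nothing forward past death.

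Cost: SAP wording, one SAS procedure with a sensitivity run, and an extra column in one table. No new patients are needed, and no new data unless the early-discontinuation assessment turns out to lack an MMSE. The interval may be slightly wider and the mean slightly less favourable.

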#### Safety

No imputation will be done on missing safety data, unless for partially incomplete dates for remote events such as AE, concomitant medication etc.

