6.1 Adverse events

An adverse event (AE) is any untoward medical occurrence (i.e., any unfavorable and unintended sign [including abnormal laboratory findings], symptom or disease) in a subject or clinical investigation subject after providing written informed consent for participation in the study. Therefore, an AE may or may not be temporally or causally associated with the use of a medicinal (investigational) product.

The occurrence of adverse events should be sought by non-directive questioning of the patient at each visit during the study. Adverse events also may be detected when they are volunteered by the patient during or between visits or through physical examination, laboratory test, or other assessments.

Abnormal laboratory values or test results constitute adverse events only if they fulfill at least one of the following criteria:

- they induce clinical signs or symptoms,
- they are considered clinically significant,
- they require therapy.

Clinically significant abnormal laboratory values or test results should be identified through a review of values outside of normal ranges/clinically notable ranges, significant changes from baseline or the previous visit, or values which are considered to be non-typical in patient with underlying disease. Investigators have the responsibility for managing the safety of individual patient and identifying adverse events. Alert ranges for labs and other test abnormalities are included in Appendix 1.

Adverse events should be recorded in the Adverse Events CRF under the signs, symptoms or diagnosis associated with them accompanied by the following information.

- the severity grade
 - mild: usually transient in nature and generally not interfering with normal activities
 - moderate: sufficiently discomforting to interfere with normal activities
 - severe: prevents normal activities
- its relationship to the study treatment (no/yes), or its duration (start and end dates) or if the event is ongoing an outcome of not recovered/not resolved should be reported.
- whether it constitutes a serious adverse event (SAE)
- action taken regarding study treatment
- whether other medication or therapies have been taken (concomitant medication/non-drug therapy)
- its outcome (not recovered/not resolved; recovered/resolved; recovering/resolving, recovered/resolved with sequelae; fatal; or unknown)

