**Version: Final 1.0 Date: 01 Dec 2022**

1. If the start date and stop date are both missing, then the most conservative approach is taken and the AE (or medication) is considered to be treatment-emergent (or concomitant medication).
2. If the start date is missing but the stop date is not missing and is on or after the day of first study dose administration, then the most conservative approach is taken and the AE (or medication) is considered to be treatment-emergent (or concomitant medication).
3. If the start date is missing but the stop date is not missing and is before the day of first study dose and after the date of signed informed consent, then the AE (or medication) is considered to be before treatment (or prior medication).
4. If the start date is not missing but the stop date is missing, then the most conservative approach is taken, and medication is considered to be concomitant while the AE is defined by the start date.

If the adverse event relationship flag is missing, the relationship for the adverse event will be imputed and will be considered as possibly related. If the Adverse Event Severity flag is missing, the severity will be imputed with the maximum severity as “Severe” and if the adverse event is flagged as Serious adverse event and the severity flag is missing then the maximum severity imputed will be “life-threatening”

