## 9.7 Safety Analysis

### 9.7.1 Adverse Events

Adverse Events will be coded using the Medical Dictionary of Regulatory Activities (MedDRA version 20.1), the coded terms will be used for summarizing the AE(s). Only treatment emergent adverse events (TEAE) will be summarized in tables, while all events will be listed. Adverse events will be analyzed using safety population.

An AE will be considered as treatment-emergent if the time of onset is on or after the time of the first dose or any AE that exist prior to first dose and if it increased in severity during the study period. Handling of missing data for AE are explained in section 8.5.1 (Imputation of missing data).

An overall summary table which summarizes, the number and percentages of patients with adverse events, serious adverse events, adverse events leading to death, adverse events related to study drug and adverse events by severity categories will be provided. All the AE tables will be summarized based on TEAE,

Patients experiencing any treatment emerging adverse events will be summarized by Preferred Term (PT) and SOC. The number and percentage of patients with at least one TEAE, SAE, discontinuation of study treatment due to death and TEAEs of severe intensity will be summarized by system organ class, preferred. Furthermore, listings of AEs, SAEs and Deaths will be provided.

Furthermore, an overall Adverse event listing will be provided, and a separate listing will be provided for AE leading to death.

AEs tables by primary system organ class and preferred term will be sorted in descending order of counts.

Also an overall AE summary table which summarizes, the number and percentages of patients with adverse events, serious adverse events, permanently discontinued study treatment, adverse events leading to death, adverse events related to study drug and adverse events by severity categories will be provided for the SAF population.

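### SAP 8.5.1 bars imputing missing safety data except partial dates, then imputes missing AE relationship and severity, for SAEs to a grade that neither the protocol nor the tables contain

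*SAP*

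**What the plan says.** The Safety part of SAP 8.5.1 opens with a general rule: "No imputation will be done on missing safety data, unless for partially incomplete dates for remote events such as AE, concomitant medication etc". Rules for partial start and end dates follow.

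The closing paragraph of the same section gives three rules for AE attributes that are not dates:

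- Relationship: "If the adverse event relationship flag is missing, the relationship for the adverse event will be imputed and will be considered as possibly related".
- Severity: "If the Adverse Event Severity flag is missing, the severity will be imputed with the maximum severity as" *Severe*.
- Severity of an SAE: "if the adverse event is flagged as Serious adverse event and the severity flag is missing then the maximum severity imputed will be" *life-threatening*.

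Protocol 6.1 defines what is collected. Relationship is recorded as "its relationship to the study treatment (no/yes"). Severity has three grades, mild, moderate and severe, and the top one is defined as "severe: prevents normal activities".

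SAP 9.7.1 plans an overall table in which "adverse events related to study drug and adverse events by severity categories will be provided", and it sends the reader to 8.5.1 for the handling of missing AE data. The shells for Tables 14.3.1 and 14.3.3 have rows for mild, moderate and severe only. The shell for Table 14.3.4 (relationship) refers to the 14.3.3 layout and lists no relationship categories.

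**The concern.** Relationship and severity are safety data and they are not dates, so the only stated exception does not cover them. As written, a programmer can follow either the general rule or the closing paragraph, but not both.

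Under SAP 9.6.1 the primary safety objective is assessed through AEs. Related-AE and by-severity summaries are named outputs in SAP 9.7.1, and Protocol 8.5.2 asks for suspected drug-related AEs and for maximum severity. The study has one arm, so these rates stand alone. A shift caused by the missing-data rule is not offset by a similar shift in a control group.

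The closing paragraph has a second problem when followed to the letter. It assigns values that are not on the protocol's scales, and for SAEs it assigns one that the table shells have nowhere to put.

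**Working it through.** **1. The two rules side by side, as the tables would show the event**

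| AE with a missing flag | General rule: no imputation | Closing paragraph, read literally |
|---|---|---|
| Relationship missing | Not counted as related | *Possibly related*: not on the protocol's no/yes scale, but most naturally counted in the related row of Table 14.3.1 |
| Severity missing, non-serious AE | In no severity row | *Severe*: counted in the Severe row |
| Severity missing, SAE | In no severity row | *Life-threatening*: not a protocol grade, no row in Tables 14.3.1 or 14.3.3 |

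The last two lines show the anomaly. With severity missing, a non-serious AE would be tabulated as severe, while a serious one could fall outside the Severe row.

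**2. Does another passage settle it?**

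- SAP 9.7.1 points back to 8.5.1 without choosing between the rules.
- Protocol 8.4.3 gives only LOCF for missing values at week 16.
- SAP section 10 lists two changes from the protocol, the added screened population and the choice of analysis population. Neither concerns AE attributes.

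**3. Size**

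The plan states no figure for this point, so there is none to reproduce. The planned sample size supplies the denominator. With p = 0.746, a relative error of 10% and z = 1.645 (90%), n = z²(1 − p)/(p × 0.10²) = 92.1, rounded up to 93, which agrees with SAP 8.6. The planned enrolment of 102 agrees with 93 × 1.1 = 102.3.

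Let k be the number of patients whose classification as having a related (or severe) AE rests only on an event with a missing flag. The two rules then differ by k/N. The documents give no value of k, so the values below are assumptions.

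| k (assumed) | N = 93 | N = 102 |
|---|---|---|
| 0 | 0 | 0 |
| 1 | 1.1 points | 1.0 points |
| 2 | 2.2 points | 2.0 points |
| 5 | 5.4 points | 4.9 points |
| 10 | 10.8 points | 9.8 points |

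For example, suppose 5 of 93 patients have a recorded severe AE (5.4%) and 5 others have only a non-serious AE with missing severity. The rate becomes 10/93 = 10.8% with imputation.

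A patient already counted through another related or severe AE does not add to k. Under the literal *life-threatening* rule, a patient whose only candidate event is an SAE with missing severity does not add to k for the Severe row either, because neither rule puts that event there.

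**4. What does not move**

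Whether a patient had any treatment-emergent AE depends on onset relative to first dose, or on worsening of an earlier event. A missing relationship or severity flag does not remove a new-onset event from that count. The overall incidence on which the sample size rests is therefore the same under both rules.

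**The case against.** The strongest reply is that the intended rule is fairly clear. The closing paragraph is specific, names its values, and is the only text in 8.5.1 that mentions these flags. A programmer would probably apply it, and it is conservative for safety. That stands as a statement of likely intent. It does not remove the conflict, because the general rule limits its exception to dates, and it does not give *life-threatening* a row in the tables.

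A second reply is that few flags may be missing. Both are required AE items under Protocol 6.1, Protocol 7.1 requires full verification of data used for primary variables, and SAP 11 places data cleaning before lock. This is fair. With k = 0 the two rules give identical tables.

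Two stronger readings are tempting, and the documents support neither.

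- A reader might infer that *possibly related* matches no category that would be counted. The 14.3.4 shell lists no categories, Table 14.3.1 has a single related row where the value would naturally fall, and the rule in SAP 9.7.1 of taking the closest relationship would also fit a graded scale. SAP 5 refers to a CRF (Final 2.0, 03 Apr 2018) that is later than the protocol (21-Dec-2016) and is not available here, so the collected categories cannot be checked.
- A reader might infer a large distortion, such as the severe-AE rate changing by half or more. That needs assumed missing rates and AE frequencies that the documents do not supply.

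The silence of SAP section 10 is also not a fault in itself. The protocol has no rule for missing AE attributes and leaves details to the SAP, so adding one does not contradict it.

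**Conclusion.** The contradiction is in the current text of one SAP section, and no other passage resolves it. If any relationship or severity flag is missing, the related-AE and severe-AE counts can depend on which sentence is followed. The difference is about 1 percentage point for each patient whose classification rests only on a missing flag. The size rests on two assumptions: a safety population close to the planned 93 to 102, and an unknown k that may be zero.

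Separately, the closing paragraph taken literally can leave an SAE with missing severity outside the Severe row. The overall AE incidence is not at risk, and no hypothesis test depends on these rates. This is a wording defect in the main safety tables, worth correcting because the correction is cheap and removes a choice that would otherwise be made after the data are seen.

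**What to change.** Make these changes before database lock:

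1. In the general rule of SAP 8.5.1, extend the exception beyond partial dates to missing AE relationship and missing AE severity, handled as specified later in the section.
2. In the closing paragraph, map each imputed value to a category that the CRF collects and the tables show. For relationship, use the related category, which is *yes* if the CRF follows the protocol's scale; check this against the CRF first. For severity, use *Severe* for every missing value, including on SAEs, and delete *life-threatening*.
3. Add a footnote to Tables 14.3.1, 14.3.3 and 14.3.4 giving the number of AEs with an imputed flag and the patient counts without imputation.

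The first two changes settle the contradiction. The third is not needed for that, but it lets a reader see at once whether imputation mattered. The cost is a few sentences of SAP text, one table footnote and a trivial extra run, with no new data collection.
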